This data supports MRI as the modality of choice for preoperative staging prior to surgery or neoadjuvant therapy. However, the ability of MRI to predict pCR accurately following preoperative CRT has not been established. MRI performed 4-6 weeks following the completion of preoperative CRT for locally advanced rectal cancer is rarely normal, even in those patients that will achieve pCR at surgery. Rather, in those patients with an optimal response on MR, a 'scar' replaces the site of disease, represented by a focal area of low-signal intensity on T2-weighted MR. The precise cellular composition of such an area of low signal intensity cannot be known, and a single MRI scan cannot diagnose complete response. However, if surgery is deferred, then the 'scar' may be monitored with serial imaging to exclude any change. By adopting this approach, the time interval to maximal tumour debulking can be established and identification of true 'complete responses' may be made (sustained radiological and clinical complete response).

2.6 18F-FDG PET/CT as a tool to confirm response to Pre-operative Chemo-radiotherapy

Some work has been undertaken to assess the ability of 18F-FDG PET/CT to predict pathological response in rectal cancer. Pathological response is graded by some histopathologists using the Mandard five-point tumour regression grading scale to assess the presence or absence of residual tumour cells²¹. TRG1 represents complete tumour regression, TRG 2 is characterised by the presence of rare residual cancer cells scattered through the fibrosis. In TRG3, fibrosis is still predominant, while TRG4 shows residual cancer outgrowing fibrosis, and TRG5 is characterised by absence of regressive changes. The relationship between this TRG score and 5 year outcomes has been examined by Vecchio et al²². The local 5 year local failure rate was 2% for TRG1-2 vs 58% for TRG3-5. The TRG also predicted the incidence of pathological nodal involvement as 91% of patients with TRG1-2 were pN0, versus 63% for TRG3-5.

Capirci et al studied 42 patients with locally advanced rectal cancer who were imaged with FDG PET before and 5-6 weeks after completion of CRT^{23} . The pretherapy SUV values were not predictive of pathological response. However, the response index (SUV_{initial} - SUV_{final})/SUV_{initial}) showed a good correlation with the Mandard tumour regression grade (TRG). A cut-off of 66% decrease in SUV allowed differentiation of

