3.0 STUDY OBJECTIVES

The primary objective of this study is to establish the time to maximum tumour response following CRT, and to investigate whether surgery can be safely avoided within the tight framework of the trial follow-up protocol in a small group of patients where the cancer becomes undetectable by imaging modalities.

It also allows the use of 18F-FDG PET/CT in combination with MRI and clinical examination (tri-modality assessment) to assess for a continued incremental response to CRT. It should be made clear that surgery is not withheld from patients entering this study. Indeed, surgery is an option at each stage of patient follow-up and is a crucial component of a patient's treatment pathway if a point is reached when there is no further regression of disease. However, should the patient refuse surgery or be medically unfit for a rectal surgery, they will continue to be followed up without surgical intervention. If a status of 'no detectable disease' by serial MRI, PET/CT and clinical assessment is achieved and the patient wishes not to have surgery, they will continue to be stringently monitored within the framework of the trial follow-up protocol.

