4.4 Treatment withdrawal criteria

- a) Patient decision to withdraw from trial and proceed to surgery
- b) Following registration, disease (that has not yet achieved a modified Mandard tumour regression grade 1 or 2; Appendix 10.2) that shows stable disease over 2 consecutive MRI scans, 4 weeks apart.

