2 has been achieved (if stable disease is demonstrated for such a patient on 2 consecutive scans during this period, the patient will be referred for immediate surgery). More frequent MRI scanning will be performed at the discretion of the MDM. A modified Mandard Tumour Regression Grade has been used for reporting (please see appendix 10.2).

The timing, indication and interpretation of biopsies is viewed as critically important in the context of this trial. Blind biopsies are discouraged, ie if there is no abnormality on sigmoidoscopy/ colonoscopy, then we do not recommend biopsies directed at the mucosa once occupied by the tumour. Biopsies are discouraged unless: i) an area of residual disease is visualised at (and no earlier than) 3-month Sigmoidoscopy; ii) a clinically suspicious area develops/re-appears at Sigmoidoscopy/colonoscopy; iii) MR changes raise the suspicion of recurrence.

Patients with evidence of clinical or radiological local recurrence will be referred immediately by phone and fax to the surgical team for urgent biopsy. It is anticipated that such concerns will be brought to light by MR imaging, and thus will automatically be discussed at the Unit MDM. If there is a clinical suspicion of recurrence from a source other than MR, then an urgent MRI will be considered depending on date of previous imaging. All such cases will be discussed at the next available MDM. If urgent salvage surgery is recommended, a PET/CT scan will be performed routinely pre-op to outrule occult metastatic disease.

Subjects with metastatic disease detected during follow-up will be treated according to the Unit MDM recommendation.

Patients with evidence of clinical or radiological local recurrence must be treated at least as urgently as a primary rectal cancer by the surgical team.

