8.0 STATISTICAL CONSIDERATIONS

Analysis methods

All time-to-event endpoints will be measured from the end date of chemoradiotherapy, and calculated using Kaplan-Meier methods. The final analysis will be carried out when all patients have had at least 2 years follow-up. An additional overall survival analysis may be carried out after all patients have had at least 10 years follow-up. **Patients who have not yet experienced the event in question will be censored at date of last follow-up**.

Primary endpoints

Since all patients will have at least two years complete follow-up, the percentage of patients in continued response without surgery at two years, and the percentage of patients with local failure at two years, will be calculated as percentages of all patients, with exact 95% binomial confidence intervals.

Secondary endpoints

Time to distant disease will be measured as the time to the first diagnosis of lymph node or other distant disease, confirmed via PET/CT, MRI, CT or pathology.

Time to maximal tumour response will be defined as follows: for patients who achieve CR, it is the time until first recorded MRI scan with tumour grade T0. In patients where this has not happened, it will be the time to the first of two consecutive MRI scans which show the same modified Mandard regression grading (or the first of two consecutive scans in which the second scan shows an increased Mandard regression grade). Patients with a continuing reduction in Mandard grade at the time of analysis will be censored at the date of last scan..Patients who opt for surgery or withdraw for other reasons before recorded maximal response will be censored at date of last scan.

Time to local regrowth will be measured as the time until the first recorded increase in Mandard grade, on MRI. Patients with continued stable disease or complete response will be censored at date of last MRI scan. Patients who opt for surgery or withdraw for other reasons before recorded local regrowth will be censored at date of last scan.

Of all patients who had surgery for progression of local disease, the percentage with positive margins will be calculated, with an exact 95% confidence interval. The percentage who had negative margins and had their sphincters preserved will also be calculated with an exact 95% confidence interval

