Progression free survival will be measured as time until the first occurrence of any of the following: increased Mandard grade (in patients who did not achieve CR), any tumour T1 or above (in patients who achieved CR), first diagnosis of nodal or distant disease (diagnosed on MRI, CT, PET or pathology); or death from any cause.

Quality of life will be measured using EORTC QLQ-C30, IBDQ and Vaizey questionnaires. Missing data will not be replaced, but numbers assessed at each time-point will be reported. Change from baseline will be assessed at each time-point and summarised using descriptive statistics. In addition, counts and percentages of LENT-SOMA worst grades at each time-point will be reported.

Sample size

We wish to show that the percentage of patients who can successfully omit surgery is at least 10%, with a true rate expected to be at least 25% (and possibly this may be considerably higher). The two-year failure rate is assumed to be no more than 5%, and a failure rate of 15% or more would be considered to be unacceptable.

Using a single-stage exact phase II design, with one-sided significance level of 0.05, then a total of 59 patients would provide 80% power to prove a 2-year failure rate of less than 15% if the true rate is no more than 5%. The trial would be a success according to this endpoint if no more than 4 patients out of 59 have local failure at 2 years. The same number of patients would provide at least 90% power to show that the proportion of patients safely omitting surgery is more than 10%, if the true rate is

expected to be at least 25%. The trial would be a success according to this endpoint if at least 11 out of 59 patients have safely omitted surgery. To be judged a success overall the trial must pass both of these endpoints (no more than 4 patients with local failure, and at least 11 safely omitted surgery).

We expect to recruit 39 patients from the Royal Marsden and network hospitals and 20 patients from other multi-centre sites. This recruitment is expecting to be completed by 31st December 2012. We believe 60% of eligible patient will wish to participate in the "deferral of surgery". However, only 20% of rectal patients who undergo pre-operative CRT will develop a complete response and meet the inclusion criteria.

Stopping Rule

The trial will be stopped if 5 patients develop disease which is surgically not

salvageable or incompletely excised. There will be continuous monitoring of all

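### The PFS event list has no event for a non-nodal pelvic recurrence, or unresectable disease found at surgery, in patients operated on without CR and without a prior grade increase

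*Protocol*

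**What the plan says.** PFS is part of secondary endpoint 5 (section 3.2) and is defined in section 8.0. Its local events are "increased Mandard grade (in patients who did not achieve CR), any tumour T1 or above (in patients who achieved CR"). The remaining events are "first diagnosis of nodal or distant disease (diagnosed on MRI, CT, PET or pathology); or death from any cause". Surgery is not an event.

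PFS has no censoring rule of its own for surgery, so the general rule of section 8.0 applies: "Patients who have not yet experienced the event in question will be censored at date of last follow-up". Time to local regrowth does have such a rule: "Patients who opt for surgery or withdraw for other reasons before recorded local regrowth will be censored at date of last scan". Time to maximal tumour response has a similar one.

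The protocol describes three routes to surgery that need neither CR nor a grade increase:

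- Section 3.0: "surgery is an option at each stage of patient follow-up". The same section describes surgery as central once regression has stopped.
- Section 7.0, for patients not yet at regression grade 1 or 2: "if stable disease is demonstrated for such a patient on 2 consecutive scans during this period, the patient will be referred for immediate surgery".
- Section 4.4, which lists as a withdrawal criterion "Patient decision to withdraw from trial and proceed to surgery" and, as a second one, stable disease on two consecutive scans in patients not at grade 1 or 2.

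**The concern.** The modified Mandard grade describes how far the irradiated primary has regressed, and section 8.0 reads it on serial MRI. Once the rectum has been resected there is no primary to grade. For a patient who never reached CR, this grade is the only local PFS event. A relapse at the anastomosis or in the presacral space then has no place in the definition unless it is nodal.

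PFS is one of the endpoints by which readers will judge the safety of deferring surgery. An event list that overlooks local relapse in some operated patients gives a more favourable curve than the data warrant. It also leaves an inconsistency. A patient whose disease proves surgically unsalvageable is a local failure for the second primary endpoint (section 3.1) and counts toward the stopping rule (section 8.0), yet can still be progression-free for PFS.

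**Working it through.** **1. The plan's own figures.** The protocol gives no figure for PFS. Its design figures reproduce by exact binomial calculation with N = 59:

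- Local failure, success if at most 4: P(X ≤ 4 | 0.15) = 0.0469 and P(X ≤ 4 | 0.05) = 0.828.
- Surgery omitted, success if at least 11: P(X ≥ 11 | 0.10) = 0.0306 and P(X ≥ 11 | 0.25) = 0.903.

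Neither calculation uses PFS, so the point below leaves the design untouched.

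**2. Each PFS event applied to one patient.** Take a patient without CR and without a grade increase who is resected and later has an isolated, non-nodal pelvic recurrence.

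| PFS event (section 8.0) | Does it occur? |
|---|---|
| Increased Mandard grade (no CR) | No: no primary tumour remains to be graded |
| Tumour T1 or above | No: restricted to patients who achieved CR |
| Nodal or distant disease | No: the recurrence is neither |
| Death | Not at that time |

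The same holds when unresectable local disease is found at the operation and the MRI grade had been stable.

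**3. What happens to the patient in the analysis.** There are two readings.

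- *Follow-up continues.* Under the general rule the patient stays at risk and progression-free until nodal or distant disease, death or last follow-up. The error can then only raise PFS.
- *Surgery is treated as withdrawal (section 4.4) and follow-up ends.* The patient is censored near surgery and the relapse is not counted. If patients whose tumours stopped regressing relapse more often than those who remain, the censoring is informative and PFS again reads too high. Under this reading the direction is likely but not certain.

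**4. Size, as an illustration of the first reading.** With complete follow-up to a fixed time,

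overstatement of PFS ≈ f × r, and patients affected ≈ 59 × f × r.

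- f is the share of patients operated on without CR or prior progression. The protocol does not give it; 10%, 25% and 50% are assumed.
- r is the risk of a non-nodal pelvic recurrence with no other PFS event by that time. The protocol does not give it. The 7.6-9.6% used here is the 5-year local recurrence as a first event in the three chemotherapy arms of the randomised trial in section 2.0.

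| f | f × r (percentage points) | 59 × f × r (patients) |
|---|---|---|
| 10% | 0.76 to 0.96 | 0.45 to 0.57 |
| 25% | 1.9 to 2.4 | 1.12 to 1.42 |
| 50% | 3.8 to 4.8 | 2.24 to 2.83 |

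This is about 0.5 to 3 patients, or about 1 to 5 points. If r is allowed to range from 2% to 20%, the result runs from 0.1 × 0.02 = 0.2 points to 0.5 × 0.20 = 10 points.

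**The case against.** Four arguments can be made against the point.

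**Other endpoints catch these patients.** Unsalvageable disease is primary endpoint 2, the stopping rule also counts incomplete excision, and disease-free survival in section 6.3 counts local progression. Pelvic nodal relapse, distant disease and death remain PFS events, so some relapses are only counted late. This is true and limits the harm, but it does not repair PFS. A salvageable local recurrence is not a primary-endpoint failure. Section 6.3 measures from the start of CRT, whereas section 8.0 measures from its end, and disease-free survival is not in the list in section 3.2.

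**The patients may not stay in the curve.** A reader might infer that every such patient is carried for years as progression-free. The documents do not establish this, because section 4.4 lists both patient choice and stable disease as withdrawal criteria. That part of the objection stands. It changes the mechanism to possibly informative censoring, but the relapse is still uncounted.

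**The effect may be small.** Two larger figures are tempting, and neither is supported.

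- Section 2.6 reports: "The local 5 year local failure rate was 2% for TRG1-2 vs 58% for TRG3-5". Applying 58% to an assumed 10 to 20 operated patients would give 6 to 12 missed recurrences. But this is a 5-year rate by pathological grade, while the trial grades on MRI and plans its final analysis once all patients have at least 2 years. Section 4.0 admits patients at grade 2, or at grade 3 moving to grade 2 by week 8, and the same sentence gives only 2% for grades 1-2.
- From the expected 25% omission rate one might infer that 59 − 0.25 × 59 ≈ 44 patients will be operated on without a countable local event. The 25% is a lower bound. The remainder also includes deaths, patients who refuse or are unfit for surgery, and patients operated on for regrowth, who already have a PFS event.

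**Unseen text.** Appendices 10.2 and 10.5 are not in the text at hand and might say more about grading and follow-up. Nothing in the visible text uses the Mandard grade after resection.

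**Conclusion.** The gap is real. The event list is closed, none of its events covers this relapse, and the protocol itself describes the routes to such surgery. It is an error in a definition that the protocol fixes, so an SAP that followed the definition would carry it forward.

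The supportable size is modest: about 1 to 5 percentage points of PFS, resting on an assumed affected share of 10-50% and on a 5-year recurrence rate borrowed from the background. That rate may be too high for an analysis at 2 years and for non-nodal relapse alone, or too low for tumours that stopped regressing. Readers might go on to doubt the primary conclusions, but the documents do not support that. PFS is secondary, and N = 59 and both primary decision rules stand. The point deserves correction before analysis and does not threaten the trial.

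**What to change.** Amend the PFS definition in section 8.0 in four respects:

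1. Add as an event, for all patients whether or not they achieved CR: *local or pelvic recurrence after rectal resection, on imaging or pathology, or unresectable local disease found at surgery*.
2. Apply the Mandard-grade and T1 criteria only to the period before resection.
3. State that operated patients remain in follow-up for PFS and are not censored at surgery. Make clear that withdrawal under section 4.4 does not by itself end PFS follow-up, unless the patient also withdraws from data collection.
4. Reconcile the definition with disease-free survival in section 6.3, including the start date, or say why both are kept.

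The cost is a few sentences. Section 7.0 already plans clinic follow-up to 10 years. PFS becomes slightly less favourable; the sample size and the primary decision rules do not change.
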